
ASSESSMENT SCHEDULE
	
Efficacy: referring to the 96-week double-blind period
 
 
• Clinical relapses.
 
• EDSS: screening, randomization, after relapse, every 24 weeks and at EOT.
 
• Cognitive battery: randomization and EOT.
 
• SDMT: randomization, every 24 weeks and at EOT.
 
• MRI: baseline (a previous MRI performed in the 6 weeks preceding randomization could be acceptable if performed according to the specifications for this study), 24, 36 (if criteria is met at Week 24), 48, 72 and 96 weeks.
 
 
Safety and tolerability: referring to the 96-week double-blind period
 
 
• AE reporting at each visit.
 
• Physical examinations: screening, randomization, Weeks 12, 24, and every 12 weeks, EOT or early treatment discontinuation and at EOT +2W.
 
• Vital signs: screening, randomization Weeks 4, 8, 12, 24, and every 12 weeks while on treatment, at EOT or early treatment discontinuation, at EOT+2W and at EOT+4W, and after relapse.
 
• Tanner stage: at baseline, every 24 weeks and EOT (until complete sexual maturity defined by Tanner Stage 5).
 
• Clinical laboratories: screening, randomization, Weeks 4, 8, 12, 16, 20, 24, then every 6 weeks up to EOT or early treatment discontinuation, at EOT + 2W and at EOT + 4W.
 

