2.1 ANALYSIS ENDPOINTS

2.1.1 Demographic and baseline characteristics

The baseline value is defined as the last available value before the first intake of IMP in the double-blind period, unless otherwise specified.

All baseline safety and efficacy parameters (apart from those listed below) are presented along with the on-treatment summary statistics in the efficacy and safety sections (see [Section 2.4.4](#) and [Section 2.4.5](#)).

Demographic characteristics

Demographic variables are gender (Male, Female), race (Caucasian/white, Black, Asian/Oriental, other), ethnicity (Hispanic or Latino, Not Hispanic or Latino), region (definition of the regions are provided in [Section 2.5.5](#)), age in years at study consent of the double-blind period (quantitative and qualitative variable: <13, and ≥ 13 years), pubertal status, Tanner staging.

Medical or surgical history

Medical (or surgical) history includes concurrent illnesses, detailed neurological history and detailed vaccination history.

This information will be coded using the version of Medical Dictionary for Regulatory Activities (MedDRA) currently in effect at Sanofi at the time of database lock.

Disease characteristics at baseline

Specific disease history includes the following:

- Time since first diagnosis of Multiple sclerosis (MS) relative to randomization (in years)
- Time since first symptoms of MS relative to randomization (in years)
- Time since most recent relapse onset relative to randomization (in months)
- MS type (relapsing remitting, progressive relapsing)
- Number of relapses experienced within past 1 year (quantitative variable and qualitative variable: 0, 1, 2 and ≥ 3)

- Number of relapses experienced within past 2 years (quantitative variable and qualitative variable: 0, 1, 2, 3 and ≥ 4)
- Number of relapses experienced overall (quantitative variable and qualitative variable: 0, 1, 2, 3 and ≥ 4)
- With previous MS medication in the last 2 years (Yes, No)
- Total number of any events since onset of MS (0, 1, 2-5 and >5) and the subtype (Non encephalopathic Central nervous system (CNS) clinical events, Acute Disseminated Encephalomyelitis (ADEM), other event).

Vital signs

Vital signs at baseline as well as extension baseline (defined as the last available value before the first intake of IMP in the open-label extension period) are weight in kilograms (quantitative variable and qualitative variable: ≤ 40 , >40), height in cm, Body Mass Index (BMI) in kg/m^2 .

Other

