2.4.4.1 Analysis of primary efficacy endpoint

Clinical relapses are defined as new or recurrent neurological symptoms not associated with fever or infection, lasting at least 24 hours, and accompanied by new objective neurological findings upon examination by the Examining Neurologist and documented by the Functional System Scores (FSS). New or recurrent symptoms that occur less than 30 days following the onset of a relapse are considered part of the same relapse.

Note that the process of confirmation of clinical relapse is different between the double-blind period and the open-label period. Confirmation in the double-blind period involves the Relapse Adjudication Panel (RAP), whereas confirmation in the open-label period is done by the investigative center. However, some analyses will combine confirmed relapses from both treatment periods, as the criteria used in the two processes are similar.

The first clinical confirmed relapse occurring from randomization in the double-blind period (including relapses during the PK run-in (8 weeks) phase) to the end of the open-label period will be included for analysis. Treatment effect as measured by the hazard ratio and its associated 95% confidence interval will be estimated using a Cox proportional-hazards model with robust variance estimation (1). Cox model will include factors for treatment group, region, pubertal status, age, and number of relapses in the year prior to randomization. The duration of time to the event will be included in the modeling to offset the lengths of individual observations. Kaplan-Meier estimates of probability of clinical relapse at Week 24, 48, 72, 96, 120, 144, 168 and 192 will be estimated. The complementary log-log transformation will be used to construct 95% confidence intervals. A Kaplan-Meier survival curve from randomization in double-blind period to the end of open-label period will be presented. A stratified log-rank test with time to first clinical relapse as the dependent variable, treatment group as a test variable, region (definition of the regions are provided in [Section 2.5.5](#)), and pubertal status as covariates will be provided as supportive.

Censoring rule

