2.4.4.3 Analysis of additional efficacy endpoint

2.4.4.3.1 Annualized relapse rate

The annualized relapse rate (ARR) is defined as the number of confirmed clinical relapses occurred during the study per patient-year. It will be analyzed in open-label period only. A confirmed clinical relapse is defined as the appearance of a new clinical sign/symptom or clinical worsening of a previous sign/symptom (one that had been stable for at least 30 days) that persists for a minimum of 24 hours in the absence of fever. Each episode of relapse must be confirmed by the treating neurologist, based on the objective assessments by an independent evaluator (the examining neurologist) by documenting either of the following:

- A) A 1-point increase in at least two FS functions, or a 2-point increase in at least one FS function (excluding bowel/bladder and cerebral) from the previous clinically stable assessment, or;
- B) An increase of at least 0.5 point in EDSS score (unless EDSS=0, then an increase of at least 1.0 point is required) from the previous clinically stable assessment.

Relapses are collected on CRF page “MS relapse”. The objective confirmation, based on the protocol-defined criteria, is reported (Yes/No) in the CRF. Only confirmed clinical relapses will be used in the analysis.

A gross estimate of annualized relapse rate for a treatment group would be the total number of relapses for patients in the treatment group divided by the sum of standardized study durations for patients in the treatment group. Total number of confirmed clinical relapses and standardized study duration will be calculated for each patient.

- Total number of confirmed clinical relapses is defined as the number of confirmed clinical relapses with onset between enrollment date of the open-label period and treatment discontinuation/completion date (same as last dose IMP intake date).
- Standardized study duration (in year) will be calculated by (last dose IMP intake date - enrollment date of the open-label period + 1) / 365.25.

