Adjusted ARR will be performed using a Poisson regression model with robust error variance that would accommodate the potential over-dispersed data appropriately. The model will include the total number of clinical relapses as the response variable, treatment group as the test variable, pubertal status, and region as covariates. In order to account for different treatment durations among subjects, the log-transformed standardized treatment duration will be included in the model as an “offset” variable for appropriate computation of relapse rate. The robust error variances can be estimated by specifying the patient identifier in the repeated statement using SAS PROC GENMOD, and this is equivalent to the Generalized Estimating Equation (GEE) model. In comparison to the regular Poisson model, the GEE estimator is robust against

violation of the correlation structure and the distributional assumptions. The treatment-by-strata and treatment-by-region interactions will be evaluated separately at the 5% level of significance by adding the corresponding interaction term to the model. If a statistically significant interaction is detected at $p < 0.05$, further investigations will be performed for the possibility of qualitative interaction.

The estimated relapse rates and 2-sided 95% confidence intervals will be provided for each treatment group. Nelson-Aalen mean cumulative function plot will be provided for descriptive purposes.

2.4.4.3.2 *Time to sustained disability progression (using EDSS)*

The time to sustained disability progression will be assessed by EDSS during the study. The first disability progression (ie, confirmed disability worsening) is defined as a sustained increase of at least 1.0 point (0.5 for subjects with baseline EDSS > 5.5) persisting for at least 24 weeks from baseline EDSS in the double-blind period of the study.

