- If a patient has no EDSS increase that meets the criteria for progression before treatment discontinuation/completion, then the patient will be considered as free of progression till the date of last during-treatment EDSS evaluation.
- If a patient has an EDSS increase that meets the criteria for progression before treatment discontinuation, all available EDSS assessments obtained during the follow-up visits will be used to serve the purpose of progression confirmation. The patient will be considered as having disability progression if the first increase during treatment period is confirmed for at least 24 weeks during the follow-up visits. If the EDSS from the follow-up visit(s) does not confirm a sustained increase or despite all possible attempts, no confirmatory EDSS assessment is obtained after withdrawal, the patient will be considered as free of disability progression until the date of last during treatment EDSS evaluation.
- If a patient has an EDSS increase that meets the criteria for progression and completes the treatment period before the progression can be confirmed, then the patient will be considered as free of progression till the date of last during-treatment EDSS evaluation.
- In rare cases, if a patient had a delayed EDSS scheduled during the open-label period but performed during the optional extension period due to the Covid-19 pandemic, then this assessment will still be considered as during-treatment EDSS evaluation. The delayed EDSS result will be considered in the sustained disability progression determination process in the open-label analysis.
- In rare cases, if a patient had a delayed EDSS scheduled during the open-label period but performed after treatment discontinuation due to the Covid-19 pandemic, then the delayed EDSS result will be used for progression confirmation purpose only.

The hazard ratio and 95%CI for teriflunomide/teriflunomide versus placebo/teriflunomide will be estimated using Cox regression model with treatment group, region and baseline pubertal status as covariates, offset by the lengths of individual observations.

The Kaplan-Meier method will be used to estimate median time (if possible) to disability progression sustained for at least 24 weeks and cumulative disability progression rates specific to each treatment group. Kaplan-Meier graphs will be generated; quartiles and point probabilities will be calculated. Interval estimates will be calculated using 95% point wise confidence intervals.

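### The open-label annualized relapse rate model leaves out age and prior-year relapses, although the SAP's time-to-first-relapse model for the same period and patients includes both

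*SAP*

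**What the plan says.** **ARR (SAP 2.4.4.3.1).** The adjusted rate comes from a Poisson regression with robust variance and a log-duration offset. Its terms are "treatment group as the test variable, pubertal status, and region as covariates". On period, the SAP says: "It will be analyzed in open-label period only". Relapses are counted from the open-label enrollment date to the last dose.

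**Time to first relapse (SAP 2.4.4.1 and 2.4.4.2.1).** For the analysis from randomization, the "Cox model will include factors for treatment group, region, pubertal status, age, and number of relapses in the year prior to randomization". SAP 2.4.4.2.1 applies the same method to first relapse from open-label enrollment to the end of open label.

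**Population.** SAP 2.4.4 puts all efficacy analyses on the efficacy population, which SAP 2.3.2 limits to patients who enrolled in open label and took at least one dose there.

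**Availability.** SAP 2.1.1 lists "Number of relapses experienced within past 1 year" as a baseline disease characteristic, both as a count and in categories. Age at consent is a demographic variable in the same section.

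**Progression (SAP 2.4.4.3.2).** The hazard ratio comes from a "Cox regression model with treatment group, region and baseline pubertal status as covariates". Baseline EDSS enters only through the event definition.

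**Status.** SAP 2.4.4 and 2.4.4.4 call all open-label efficacy analyses exploratory and warn against confirmatory use of p-values.

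**The concern.** ARR and time to first relapse from open-label enrollment describe relapses in the same patients over the same period and will be read side by side. One is adjusted for age and relapse history and the other is not. The SAP treats relapse history as prognostic elsewhere: it is in the first-relapse model, and two or more relapses in the past year is part of the high-disease-activity subgroup (SAP 2.4.5.1).

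Two things are at stake. First, leaving out a prognostic baseline value gives up some precision. Second, the groups compared are no longer the randomized groups. Under Protocol 5.1, patients enter open label after a confirmed relapse following the run-in, after high MRI activity, or on completing 96 weeks. Treatment can influence all three routes, so randomization does not guarantee balance in relapse history among those who enter.

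**Working it through.** The documents give no expected ARR, rate ratio or precision, so there is no plan figure to reproduce. The sample size of 165 belongs to the double-blind endpoint and does not enter here.

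**1. Covariate lists side by side**

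| Analysis | Region | Pubertal status | Age | Prior-year relapses |
|---|---|---|---|---|
| First relapse from randomization (SAP 2.4.4.1) | yes | yes | yes | yes |
| First relapse from open-label enrollment (SAP 2.4.4.2.1, same method) | yes | yes | yes | yes |
| Lesion counts (SAP 2.4.4.2.3) | yes | yes | yes | no |
| ARR (SAP 2.4.4.3.1) | yes | yes | no | no |
| Progression (SAP 2.4.4.3.2) | yes | yes | no | no |

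No model in the SAP includes baseline EDSS.

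**2. ARR with moderately prognostic prior relapses**

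All inputs are assumptions: 50 placebo/teriflunomide and 100 teriflunomide/teriflunomide patients, 0.35 relapses per year in the former, true rate ratio 0.80, gamma overdispersion 0.5, mean open-label duration about 2.2 years, log rate ratio b per prior relapse of 0.2 or 0.4, and 600 simulated trials per row. Shift is the difference in mean prior relapses, teriflunomide/teriflunomide minus placebo/teriflunomide. Efficiency gain = (unadjusted SE / adjusted SE)² − 1.

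| b | Shift | Unadjusted rate ratio | Adjusted rate ratio | Efficiency gain |
|---|---|---|---|---|
| 0.2 | 0 | 0.801 | 0.802 | 1.4% |
| 0.2 | −0.2 | 0.765 | 0.794 | −0.2% |
| 0.2 | −0.4 | 0.748 | 0.810 | −4.9% |
| 0.4 | 0 | 0.802 | 0.802 | 6.4% |
| 0.4 | −0.2 | 0.728 | 0.785 | 4.2% |
| 0.4 | −0.4 | 0.686 | 0.801 | 0.3% |

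- Balanced groups: there is no bias. The variance falls by 1 − 1/1.014 = 1.4% to 1 − 1/1.064 = 6.0%. A second set of runs at b = 0.4 gave an efficiency gain of 7.3%, so the upper end carries about a percentage point of simulation noise.
- Unequal groups: the unadjusted ratio should be near 0.80 × exp(b × shift). That is 0.80 × exp(−0.04) = 0.769 at the mild end and 0.80 × exp(−0.16) = 0.682 at the strong end, in line with the simulated 0.765 and 0.686. The adjusted ratio stays at 0.79 to 0.81. The precision gain shrinks or turns slightly negative, so the benefit here is less bias.
- The sign of the shift is also assumed. With the opposite sign the unadjusted ratio would move to 0.80 × exp(0.04) = 0.833 up to 0.80 × exp(0.16) = 0.939.

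**3. ARR with a strong shared patient-level rate**

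Assumptions: 150 patients 1:2, 0.35 relapses per year, between-patient variance 0.5, 1.0 or 1.5, prior-year relapses generated by the same patient rate, at least one prior relapse, and 1,500 simulated trials per scenario. Adjusted/unadjusted SE ratios were 0.962, 0.944 and 0.892, so the SE falls by 3.8%, 5.6% and 10.8%. As sample-size equivalents, 1/0.962² = 1.08, 1/0.944² = 1.12 and 1/0.892² = 1.26. A separate check of the same set-up, including a version with the relapse-history rule in Protocol 6.2, gave a fall of 3% to 8%.

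**4. Progression with and without baseline EDSS**

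Assumptions: true hazard ratio 0.70, balanced groups, 400 simulated trials per row.

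| Log hazard ratio per EDSS point | HR without | HR with | SE without | SE with |
|---|---|---|---|---|
| −0.3 | 0.717 | 0.714 | 0.362 | 0.364 |
| 0.3 | 0.695 | 0.693 | 0.358 | 0.360 |
| 0.5 | 0.667 | 0.652 | 0.350 | 0.354 |

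The estimates differ by at most 0.015 and the SE is essentially unchanged.

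**The case against.** **The short list has a basis in the design.** Randomization was stratified by country and pubertal status, and region with pubertal status is the set used in the stratified log-rank tests. This explains a design-based list. It does not explain why the first-relapse Cox models, which are equally exploratory, carry two more terms.

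**ARR output is by group.** SAP 2.4.4.3.1 lists group rates with intervals and no rate ratio, and both groups take teriflunomide in open label. This limits the importance but does not remove the point: treatment is named as the test variable, and its interactions are tested at the 5% level.

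**The covariate may be stale.** For patients who complete 96 weeks, the prior-year count describes a year that ended nearly two years before open label, with treatment or placebo in between. This stands, and it is why the larger precision gains should not be taken as the expected case.

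**Stronger readings a reader might infer**

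- *That disagreement between ARR and first relapse could come from covariates alone.* The two already differ in counting all events rather than the first, in modelling a rate rather than a hazard, and in the explicit functional-system and EDSS thresholds that SAP 2.4.4.3.1 adds to the relapse definition. Covariates are one more source of difference.
- *That the omission costs the equivalent of 8% to 26% of patients.* That needs a strong shared patient-level rate, between-patient variance up to 1.5, and a prior-year relapse in everyone. The documents support none of these. Protocol 6.2 also admits patients with two relapses in 24 months, and SAP 2.1.1 keeps a zero category for the past year.
- *That leaving baseline EDSS out of the progression model is the same inconsistency.* No SAP model adjusts for it. With treatment, four region terms and pubertal status already in the model, adding EDSS and age makes eight parameters. If there were 20 to 40 progression events (an assumption; no count is given), that is 2.5 to 5 events per parameter.

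**Conclusion.** The point holds for ARR. Its model omits age and prior-year relapses, while the SAP's first-relapse model for the same open-label period and population includes both, and no reason is given.

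The precision gain is modest: roughly 1% to 6% lower variance with balanced groups and moderately prognostic prior relapses, and up to about an 11% lower SE of the log rate ratio under strong assumptions. Adjustment also protects against imbalance in relapse history after selective entry. In the illustration, a difference of 0.2 to 0.4 prior relapses moves a true ratio of 0.80 to between 0.69 and 0.77 unadjusted. The size and direction of any real imbalance are not in the documents, so this shows exposure to bias, not demonstrated bias. No gain from age alone was simulated; the case for adding it is consistency with the other models.

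Because ARR is an additional, exploratory endpoint, the effect is on precision and comparability. No confirmatory conclusion and no stated sample size, power or alpha changes. The absence of baseline EDSS from the progression model is not an internal inconsistency, and simulation with balanced groups shows essentially no gain from adding it.

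**What to change.** In SAP 2.4.4.3.1, add age and the number of relapses in the year before randomization to the Poisson model, keeping the offset and robust variance. The open-label relapse analyses would then share one covariate list. If the shorter list is intended, state why.

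The cost is one line and two parameters, with no new data. Under the assumptions in step 2 the model would have about 50 × 0.35 × 2.2 + 100 × 0.35 × 0.80 × 2.2 = 100 relapses for eight parameters, which is ample. SAP Section 3 includes ARR in the interim open-label report, so if that has been run, keep the shorter model as a sensitivity analysis and date the change.

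Baseline EDSS (continuous) in the progression Cox model can be offered as an optional sensitivity analysis if the number of events allows.

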EOT = end of treatment (EOT= First visit after last study drug intake), EDSS = expanded disability status scale, FS = functional score, BVMTR = brief visuospatial memory test-revised, SDMT=symbol digit modalities test, MRI = magnetic resonance imaging, PK = pharmacokinetic

- a Recommended windows: The window for obtaining biological samples at any given visit will be ±7 days. All other treatment period assessments should be completed within ±7 days of the scheduled visit date relative to the randomization visit. Post drug elimination follow-up visits should be ±7 days of scheduled visit relative to end of treatment.
- b Randomization visit up to 28 days from signing of informed consent.
- c End-of-treatment and premature discontinuation visit. This visit does not need to be performed when the patient switches to the open label period after a confirmed relapse or high MRI activity (as per protocol criteria). The drug elimination procedure must be initiated at this visit if applicable.

- d* For discontinuing treatment, 2 post drug elimination follow up visits should be scheduled 2 weeks and 4 weeks after study medication discontinuation and initiation of the drug elimination procedure. All patients who prematurely and permanently discontinue study medication will be asked to continue until the planned end of double-blind period.
- e* Re-consent must follow any RAP confirmed MS relapse for continuing in study when occurrence during PK run-in, for switching into open-label period when occurrence after PK run-in.
- f* To be prescribed at Visit 1 and report checked at Visit 2. MRI scan performed within 6 weeks prior to randomization can be used as the baseline MRI if performed according to the operations manual and accepted by the central reader.
- g* During the adverse event reporting process, specific questions about pulmonary symptoms and peripheral neuropathy symptoms will be asked. (Patients will be instructed to alert the treating physician of symptoms suggestive of immunodeficiency).

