2.4.4.2.6 Disease free patient

Disease-free patients were defined as patients with

- No confirmed clinical relapse.
- No 24-week sustained disability progression (≥ 0.5 -point EDSS score increase if baseline EDSS score > 5.5 or ≥ 1 -point EDSS score increase from baseline if baseline EDSS score ≤ 5.5 , persisting for ≥ 24 weeks).
- Free of MRI activity: No Gd-enhancing T1 lesions and no new/enlarging T2 lesions.

Alternative definitions of disease-free status, eg, using cognitive information may be additionally explored.

The proportion of disease-free patient at Weeks 48, 96, 144 and 192 will be summarized based on all patients having an MRI at these time points. Kaplan-Meier methods will be used for estimation.

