The minimum EDSS increase used to define disability progression is referred to as “minimum increase” in the following text. The initial EDSS increase that meets this “minimum increase” criterion is referred to as “the onset”. An EDSS measurement at or after 24 weeks following the onset is necessary to confirm the initial increase and is referred to as “24-week EDSS confirmation”. All EDSS measurements (with or without relapse) will be used to determine the onset of a disability progression. However, for the purpose of confirmation, only EDSS measured more than 30 days after the onset of a confirmed relapse will be used to avoid a confirmation caused by a temporary relapse. In order to confirm that the EDSS increase is persistent for at least 24 weeks, the following conditions have to be satisfied: (1) The 24-week EDSS confirmation needs to maintain at least the minimum increase; (2) all EDSS measurements between the onset and the 24-week EDSS confirmation need to maintain at least the minimum increase. Once a disability progression is confirmed, time to disability progression is defined as “date of onset - date of randomization (in the double-blind period) + 1”. If a patient has no disability progression on or before last during treatment EDSS evaluation, then the patient is considered as disability progression free until the date of last during treatment EDSS evaluation. The last during treatment EDSS evaluation is defined as last measurement during treatment period (measurement at last scheduled visit for patients who complete the treatment, or measurement at the close-out visit for patients who discontinue the treatment).

If a patient dies for any reason without a 24-week EDSS confirmation, the disability progression will be considered as confirmed with the date of the onset as the date of progression unless any EDSS measured within the 24 weeks did not maintain the minimum increase. Death due to MS (EDSS=10) will be counted as confirmed progression. The progression date is the date of death if there is no prior qualifying EDSS increase and it is the date of the first qualifying EDSS increase if there is such an EDSS increase prior to the death. All the derivation will be based on the exact EDSS evaluation date. Since the actual visit may have been ± 7 days from the scheduled visit, a -7 days window will be used to define the period of 24 weeks.

Censoring rules

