Week (W) ^a	W102	W108	W114	W120	W126	W132	W138	W144	W150	W156	W162	W168	W174	W180	W186	W192/ EOT ^{b, u}	EOT +2W	EOT +4W	Relapse visit
Visit number ^r	20	21	22	23	24	25	26	27	28	29	30	31	32	33	34	35	36 ^c	37 ^c	
Treatments																			
Concomitant medications	X	X	X	X	X	X	X	X	X	X	X	X	X	X	X	X	X	X	X
Dispense study drugs/IVRS call		X		X		X		X		X		X		X		X ^t			
Accountability/co compliance		X		X		X		X		X		X		X		X			
Teriflunomide PK sampling ^k																X	X ^l	X ^l	

EOT = end of treatment (EOT= First visit after last study drug intake), EDSS = expanded disability status scale, FS = functional score, BVMTR = brief visuospatial memory test-revised, SDMT=symbol digit modalities test, MRI = magnetic resonance imaging, PK = pharmacokinetic.

- a The open label period starts by the transition visit. It is recommended that there is no time gap between the 2 periods, or as short as possible and if possible less than 2 weeks. In case of start of the open label period at the end of the 96 weeks of the double-blind period, the transition visit will generally coincide with the EOT visit of the double-blind period. Recommended windows: The window for obtaining biological samples at any given visit will be ±7 days. All other treatment period assessments should be completed within ±7 days of the scheduled visit date relative to the transition visit. Post drug elimination follow-up visits should be ±7 days of scheduled visit relative to end of treatment.
- b End-of-treatment and premature discontinuation visit.
- c For patients discontinuing treatment, 2 post drug elimination follow up visits should be scheduled 2 weeks and 4 weeks after study medication discontinuation and initiation of the drug elimination procedure. When applicable patients who prematurely and permanently discontinue study medication will be asked to continue until the planned end of double-blind period (ie, 96 weeks after randomization).
- d Re-consent before starting open-label period and after confirmed MS relapse and when patients turn adults as per local regulations.
- e During the adverse event reporting process, specific questions about pulmonary symptoms and peripheral neuropathy symptoms will be asked. (Patients will be instructed to alert the treating physician of symptoms suggestive of immunodeficiency).

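### The -7-day allowance in the 24-week confirmation of disability progression covers one moving visit, not two, so some on-schedule EDSS pairs cannot confirm

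*SAP*

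**What the plan says.** SAP section 2.4.4.3.2 defines sustained progression as an EDSS increase that persists for at least 24 weeks. On confirmation it states: "An EDSS measurement at or after 24 weeks following the onset is necessary to confirm the initial increase". Every value between onset and confirmation must also hold the minimum increase. The dates are actual dates, not nominal visits: "All the derivation will be based on the exact EDSS evaluation date". One tolerance is given, with its reason: "Since the actual visit may have been ± 7 days from the scheduled visit", therefore "a -7 days window will be used to define the period of 24 weeks".

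EDSS is scheduled at 24-week intervals (Protocol, Clinical Trial Summary): "EDSS: screening, randomization, after relapse, every 24 weeks and at EOT". The visit windows are fixed from a common origin, not from the preceding visit:

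- Double-blind period (Protocol 1.2, footnote a): "All other treatment period assessments should be completed within ±7 days of the scheduled visit date relative to the randomization visit".
- Open-label period (SAP Appendix C, footnote a): "All other treatment period assessments should be completed within ±7 days of the scheduled visit date relative to the transition visit".

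Once confirmed, the event is dated at onset. Under the censoring rules of 2.4.4.3.2, a patient who completes treatment with an increase not yet confirmed is censored as progression-free at the last on-treatment EDSS. SAP section 2.4.4.2.6 uses the same criterion as one component of disease-free status: "No 24-week sustained disability progression".

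**The concern.** The SAP gives the visit window as the reason for the allowance, so the evident aim is that a patient seen on schedule should not miss confirmation through visit timing. An allowance of 7 days meets that aim only if one of the two dates is fixed. When both visits may move, a late onset visit followed by an early confirming visit shortens the interval by up to 14 days.

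A patient whose increase is present at two consecutive compliant visits can then remain unconfirmed. If a later EDSS exists and still shows the increase, nothing is lost. Otherwise the patient is censored as progression-free, and may also be counted as disease-free if there is no relapse and no MRI activity. The hazard ratio and the Kaplan-Meier progression rates are computed from the events that remain.

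**Working it through.** **Inputs**

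- Required interval: 24 weeks = 168 days (SAP 2.4.4.3.2).
- Allowance: 7 days, so the threshold is 168 - 7 = 161 days (SAP 2.4.4.3.2).
- Scheduled EDSS spacing: 168 days (Protocol, Clinical Trial Summary).
- Visit window: ±7 days from randomization or from transition (Protocol 1.2 and SAP Appendix C, footnotes a).

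**Formula.** Let *a* be the shift of the onset visit and *b* the shift of the next visit, each a whole number from -7 to +7. Then gap = 168 + *b* - *a*.

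**Reproducing the SAP's 7 days.** If the onset visit is fixed (*a* = 0), the smallest gap is 168 - 7 = 161 days and every in-window visit confirms. This applies when onset is at the transition visit, which anchors the open-label schedule and generally coincides with the double-blind end-of-treatment visit for patients who complete 96 weeks.

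**Both visits moving.** The smallest gap is 168 - 7 - 7 = 154 days and the largest 168 + 7 + 7 = 182. Confirmation fails when *a* - *b* is 8 or more. Of the 15 × 15 = 225 date pairs, those with *a* - *b* = 8, 9, …, 14 number 7 + 6 + 5 + 4 + 3 + 2 + 1 = 28.

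| Allowance | Threshold (days) | Failing pairs | Share if uniform |
|---|---|---|---|
| none | 168 | 105 of 225 | 46.7% |
| -7 days | 161 | 28 of 225 | 12.4% |
| -14 days | 154 | 0 of 225 | 0% |

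**Dependence on visit timing (assumed; not in the documents).** With the -7-day rule, the failing share is 5.1% for a triangular spread over ±7 days. For normal deviations truncated at ±7 days it is 0.4%, 3.1% and 6.2% for SDs of 2, 3 and 4 days.

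**Example of a loss.** A patient completes 96 double-blind weeks, so open-label Week 96 is the last visit. The target days for open-label Weeks 72 and 96 are 505 and 673 (SAP Table 5). EDSS rises on day 505 + 7 = 512 and is still raised on day 673 - 7 = 666. The gap is 666 - 512 = 154 days. Both visits are in window, the increase is not confirmed, and the patient is censored as progression-free.

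**If another visit follows.** The next scheduled EDSS falls 336 ± 14 = 322 to 350 days after onset, about 48 weeks. If all values hold, it confirms, and the event is dated at the original onset.

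**Share of onsets lost.** Assume eight scheduled EDSS visits to Week 192, permanent worsening, and onsets spread evenly over the seven visits that have a successor. Only an onset at the next-to-last visit can then be lost: 12.4% / 7 = 1.8% under uniform timing. For SDs of 2, 3 and 4 days, 0.4%, 3.1% and 6.2% divided by 7 give about 0.1%, 0.4% and 0.9%. Increases that reverse between about 24 and 48 weeks would add to this; the documents give no basis for sizing that part.

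**The case against.** The strongest reply is that the endpoint is hardly affected. The event is dated at onset and any later EDSS may confirm it, so most failures at the next visit are made good without changing the data. This is right, and it limits the harm to lost events. A reader might infer that progression itself is put back to 48 weeks; only the confirmation is. A reader might also take 12.4% as the share of progressions lost; it is the share of date pairs that fail under one timing assumption.

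Other parts of the reply also stand:

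- The problem does not arise for the interval that starts at the transition visit.
- Protocol 10.3.2 provides EDSS about every 12 weeks after early discontinuation, to the planned end of the double-blind period, which can confirm some cases. EDSS at relapse visits helps less: it is due within 7 days, and values within 30 days of a confirmed relapse cannot be used for confirmation.
- Both groups share the same schedule and windows, so nothing in the documents suggests a bias between groups.
- Neither document gives an expected number of progressions, so a claim that an already small event count is being depleted has no support.
- Failure to confirm changes disease-free status only in patients who also have no relapse and no MRI activity.

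Finally, one can defend 161 days as a deliberately strict floor of 23 weeks. That would be a legitimate choice, but it is not the reason the SAP gives. The stated reason is visit movement, and on that reason 7 days falls short.

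**Conclusion.** The defect is real and minor. The allowance does not do what the SAP introduces it to do: when neither visit is the anchor, in-window gaps of 154 to 160 days fail a 161-day threshold, and I found no other provision that covers two moving visits. The arithmetic of the gap rests only on the documents. The frequency does not; it depends on how visits scatter within the window, which the documents do not describe.

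The consequence is a lost event when the failing visit is the last EDSS, or when the increase is no longer present at about 48 weeks. The first route takes roughly 2% of onsets or less, under the assumptions shown. Time to sustained disability progression is an added endpoint in open-label analyses that the SAP treats as exploratory (2.1.3.3, 2.4.4), and disease-free status is itself labelled exploratory (2.1.3.2). No confirmatory conclusion is at risk.

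**What to change.** In SAP 2.4.4.3.2, replace the -7-day allowance by -14 days, so that an EDSS 154 days or more after onset can confirm. Alternatively, accept confirmation at the next scheduled 24-week EDSS visit or later, provided it was performed within its window. State that the same rule applies to the progression component of disease-free status in 2.4.4.2.6.

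The change is one number, or one sentence, in the SAP and the matching line in the derivation program. The downside is that an increase documented over 154 to 160 days, as little as 22 weeks, would count as 24-week progression. The current rule already accepts 161 to 167 days.
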